7.3 Visit Time Windows

[Table 1](#) presents the assigned target study day and study day window for each study period. Movement disorder frequency and duration recorded on diary will be mapped to specified period according to [Table 1](#) and actual visit days. For other scheduled efficacy and safety assessments the visit window assigned and the corresponding target treatment days during which an actual visit may occur is specified in [Table 2](#).

Table 1: Visit Mapping Window for Movement Disorder Diary

Period		Planned Duration	Target Study Day	Study Day Window
Run-In		6 weeks	[-42, 0]	<1
DB Treatment Period I	Titration	2 weeks	[1,15]	[1, 15]
	Maintenance	8 weeks	[16,71]	For subjects who entered into washout period: [study day of first dose in Treatment Period I+15, the end of Treatment Period I]; For subjects who did not enter into washout period: \geq study day of first dose in Treatment Period I+15
Washout		2 weeks	[72,85]	For subjects who entered into Treatment Period II ^[1] : [the end of Treatment Period I+1, study day of first dose in Treatment Period II-1]; For subjects who did not enter into Treatment Period II: \geq the end of Treatment Period I +1
DB Treatment Period II	Titration	2 weeks	[86,99]	[study day of first dose in Treatment Period II, study day of first dose in Treatment Period II+14]
	Maintenance	8 weeks	[100,155]	For subjects who entered into extension period: [study day of first dose in Treatment Period II+15, the end of Treatment Period II]; For subjects who did not enter into OLE period: \geq study day of first dose in Treatment Period II+15
OLE Period	Week 34	12 weeks	[156, 281]	[study day of first OLE dose date, 281]
	Week 46	12 weeks	[282,365]	[282,365]
	Week 58	12 weeks	[366, 449]	[366, 449]
	Week 70	12 weeks	[450, 533]	[450, 533]
	Week 82	12 weeks	[534, 617]	[534, 617]
	Week 94	12 weeks	[618, 701]	[618, 701]
	Week 106	12 weeks	[702, 785]	[702, 785]
	Week 118	12 weeks	[786, 869]	[786, 869]
	Week 130	12 weeks	[870, 953]	[870, 953]
	Week 142	12 weeks	[954, 1037]	[954, 1037]
	Week 154	12 weeks	[1038, 1121]	[1038, 1121]
	Week 166	12 weeks	[1122, 1205]	[1122, 1205]
	Week 178	12 weeks	\geq 1206	\geq 1206

[1] Enter into treatment Period II is defined as subjects having taken any Treatment Period II dosing

[2] Enter into OLE phase is defined as subjects having taken any OLE phase dosing.

Table 2: Visit Window for Other Scheduled Efficacy and Safety Assessments

Period	Study Week	Treatment Week	Target Day	Study Day Window
DB Treatment Period I	Study Week 0	Trt Week 0	1	≤1
	Study Week 2	Trt Week 2	15	[2, 15]
	Study Week 10	Trt Week 10	71	For subjects who entered into Treatment Period II ^[1] : [16, 78] For subjects who did not enter into Treatment Period II: ≥16
DB Treatment Period II	Study Week 12	Trt Week 0	85	[79, study day of first dose in Treatment Period II]
	Study Week 14	Trt Week 2	99	[study day of first dose in Treatment Period II+1, study day of first dose in Treatment Period II+15]
	Study Week 22	Trt Week 10	155	For subjects who entered into OLE period ^[2] : [study day of first dose in Treatment Period II+16, the end of Treatment Period II]; For subjects who did not enter OLE period: ≥study day of first dose in Treatment Period II+16
OLE Period	Study Week 34		239	[study day of first OLE dose date, 281]
	Study Week 46		323	[282,365]
	Study Week 58		407	[366, 449]
	Study Week 70		491	[450, 533]
	Study Week 82		575	[534, 617]
	Study Week 94		659	[618, 701]
	Study Week 106		743	[702, 785]
	Study Week 118		827	[786, 869]
	Study Week 130		911	[870, 953]
	Study Week 142		995	[954, 1037]
	Study Week 154		1079	[1038, 1121]
	Study Week 166		1163	[1122, 1205]
Study Week 178		1247	≥1206	

[1] Enter into treatment Period II is defined as subjects having taken any Treatment Period II dosing

[2] Enter into OLE phase is defined as subjects having taken any OLE phase dosing.

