At the end of the Run-in Period, eligible subjects will be randomized (1:1 ratio) to one of two treatment sequences (UX007/placebo or placebo/UX007). At Randomization, subjects will begin a 10-week double-blind Treatment Period 1. Treatment Period 1 will consist of a 2-week titration period and an 8-week Maintenance Period. At the end of Treatment Period 1, subjects will discontinue treatment and begin a 2-week washout period to minimize any potential carryover effect. Subjects will crossover to the second randomized, double-blind treatment assignment (placebo to UX007, UX007 to placebo) for an additional 10 weeks during Treatment Period 2. Treatment Period 2 will consist of a 2-week titration period and an 8-week Maintenance Period. At the end of the blinded crossover period (Week 22), all active subjects will have the option of rolling into the open-label Extension Period, to continue UX007 treatment for up to 3 years or until one of the following occurs: the subject withdraws consent, the subject is discontinued from the study at the discretion of the Investigator, the study is terminated, or until commercial availability of the study drug in a subject's region, whichever occurs first. Long-term safety and maintenance of effect of UX007 will be assessed during the open-label Extension Period. A study schematic is provided in Figure 2.1. A Safety Follow-up Phone Call will be conducted 30-35 days after the last dose of UX007G-CL301 study drug.

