5.6 Movement Disorder Frequency and Total Duration

For analyses, movement disorder frequency and total duration in hours will be normalized to a 4-week rate at each of the specified period:

$$\frac{\text{total number of movement disorders during the specified period} \times 28}{\text{number of days with diary data during the specified period}}$$

$$\frac{\text{total duration of movement disorders during the specified period} \times 28}{\text{number of days with diary data during the specified period}}$$

Mean duration in hours at each of the specified period is defined as:

$$\frac{\text{total duration of movement disorders during the specified period}}{\text{total number of movement disorders during the specified period}}$$

The percentage of movement disorder free days is defined as

$$\frac{\text{total number days with of zero movement disorder}}{\text{number of days with diary during the specified period}} * 100\%$$

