8.8 Efficacy Analyses

Efficacy analyses will be based on the Full Analysis Set, unless otherwise specified.

Section 10.1 Appendix A summarizes the analysis strategy for efficacy endpoints.

For weighted ANCOVA analysis, weight will be calculated by using number of non-missing diary days divided by the planned maintenance period duration (8 weeks). For Wilcoxon rank-sum test, the difference between responses of Treatment Period 1 and Period 2 will be ranked to make the non-parametric comparison between two treatment groups.

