8.8.1 Analyses of Primary Efficacy Endpoint

The primary endpoint is the frequency of movement disorder events during the maintenance treatment period. In the event of electronic diary failure, the back-up paper diary might be used during the days with missing data from electronic diary. Combined electronic diary data and paper diary data will be used.

The primary analysis will be performed using a weighted ANCOVA model, with study baseline frequency of movement disorder as a covariate, treatment sequence, treatment group and period as fixed effects, and a random effect for subject within the sequence.

After study unblinding, the normality assumption of ANCOVA model will be examined by using the Wilk-Shapiro test on the residuals from the ANCOVA model (Shapiro et al. 1965). When there is strong evidence suggesting that the normality assumption is not met (p value for Wilk-Shapiro test < 0.05) (Normadiah 2011) (Yap et al. 2011), Wilcoxon rank-sum test will be considered as the primary analysis to assess treatment difference in movement disorder event frequency.

The following sensitivity analyses will be performed.

- To analyze the percent change from study baseline in the frequency of movement disorder during the maintenance period, the primary weighted ANCOVA model will be performed.
- Wilcoxon rank-sum test will be performed to assess treatment difference in movement disorder event frequency.
- The primary weighted ANCOVA based on the frequency of movement disorder events will be performed based on Per Protocol Set.
- In case paper diary is used as back up, sensitivity analysis excluding paper diary will be considered. The primary weighted ANCOVA based on the frequency of movement disorder events will be performed.
- If subjects discontinued during the 2-week titration period or missed one treatment period entirely, impute the movement disorder frequency during the maintenance period using the frequency during the titration period if titration period data is available, otherwise, the study baseline will be used to impute the movement disorder frequency during the maintenance period. Then the ANCOVA model based on the frequency of movement disorder events during maintenance phase will be performed, with study baseline frequency of movement disorder as a covariate, treatment sequence, treatment group and period as fixed effects, and a random effect for subject within the sequence.

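### SAP Table 1 gives the Period II Maintenance window no end for subjects who take no extension dose, and its Period I rows overlap for dropouts, so off-drug diary days after the planned 8 weeks can enter the primary rate (minor).

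*SAP*

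**What the plan says.** SAP 1 describes the primary endpoint as event frequency over eight weeks of maintenance treatment. SAP 7.3, Table 1 plans Maintenance as 8 weeks, with target study days 16 to 71 and 100 to 155. Diary days are assigned by a separate column, the study day window:

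- **Period II Maintenance.** Subjects who entered the extension have a window from first Period II dose + 15 to the end of Treatment Period II. The other row, "For subjects who did not enter into OLE period", gives only the lower limit. The footnote reads "Enter into OLE phase is defined as subjects having taken any OLE phase dosing", and the extension is optional: "all active subjects will have the option of rolling into the open-label Extension Period" (Protocol synopsis).
- **Period I Maintenance.** Subjects who entered washout have a closed window. The other row, "For subjects who did not enter into washout period", again gives only a lower limit.
- **Washout.** Subjects who did not enter Treatment Period II have every day from the day after the end of Treatment Period I.

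SAP 5.6 divides the events by the "number of days with diary data during the specified period" and scales to 28 days. SAP 8.8 sets the ANCOVA weight to non-missing diary days over 8 weeks, that is, days/56, with no stated maximum. SAP 7.2 presents observed data only. Nothing stops diary data at the last dose or at the planned end of the period.

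**The concern.** Whether days beyond the planned 8 weeks count in the primary endpoint depends on whether the subject took a dose in the next phase, which has nothing to do with what the endpoint measures.

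Off-drug entries are foreseeable. Protocol 7.3.3 allows the Early Termination visit up to four weeks after discontinuation, and Protocol Table 2.3 marks symptom diary completion at that visit. For a Period II discontinuer such entries are Maintenance days under Table 1 as printed, including those after period day 71.

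For a Period I dropout the table gives two answers. That subject did not start Period II, so the Washout row applies. If the subject also did not enter washout, the open Maintenance row applies to the same days. The footnotes define entry into Period II and into the extension. They define neither entry into washout nor the end of Treatment Period I.

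One programmer could follow the window column and another the target days, and they would build different primary datasets. Choosing between them after unblinding would be a data-dependent decision on the primary endpoint.

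**Working it through.** **Inputs from the documents.** Rates of 8 (placebo) and 4 (UX007) per 4 weeks, SD of the difference 7.4, 20 subjects per sequence and 15% discontinuation (SAP 3.6). Early Termination up to 28 days after stopping (Protocol 7.3.3). Maintenance runs over period days 16 to 71, which is 56 days; period day 71 is study day 155 if Period II starts on Day 85, the Week 12 target day in Table 2.

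**Assumptions.** Immediate return to a rate of 8 off drug, every off-drug day recorded, and within-subject correlation 0.3 to 0.7. The documents give none of these.

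**The plan's own figure.** 40 × 0.85 = 34 evaluable subjects. With a difference of 4 and SD 7.4, two-sided 0.05, noncentral t power is 86.4%, which agrees with the stated minimum of 85%. The yardstick is SE = 7.4/√34 = 1.27.

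**One UX007 record.** For last dose on period day L and g recorded off-drug days:

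- days counted = L + g − 15
- weight = (L + g − 15)/56
- rate = (on-drug days × 4 + off-drug days × 8)/(all days)

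| L | g | Days | Rate, weight as written | Rate, weight if ended at day 71 |
|---|---|---|---|---|
| 57 | 28 | 70 | (42×4 + 28×8)/70 = 5.60, 1.25 | (42×4 + 14×8)/56 = 5.00, 1.00 |
| 70 | 28 | 83 | (55×4 + 28×8)/83 = 5.35, 1.48 | (55×4 + 1×8)/56 = 4.07, 1.00 |
| 57 | 7 | 49 | (42×4 + 7×8)/49 = 4.57, 0.875 | unchanged |
| 70 | 7 | 62 | (55×4 + 7×8)/62 = 4.45, 1.11 | 4.07, 1.00 |

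The end date matters only when L + g > 71. With g = 28 that means a last dose on day 44 or later.

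**Effect on the treatment difference, one Period II dropout.** With 20 per sequence and equal weights, one record moves the estimate by 1/40 of its own shift. Ended at day 71, the difference is 4 − 1.00/40 = 3.975 (L = 57) or 4 − 0.07/40 = 3.998 (L = 70). As written, the expected generalised least squares estimate was used, with sequence, period, treatment and random subject, and residual variance proportional to 1/weight. The baseline covariate was left out.

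| L, g | As written | Ended at day 71 | Gain |
|---|---|---|---|
| 57, 28 | 3.953–3.955 | 3.975 | 0.020–0.022 |
| 70, 28 | 3.956–3.959 | 3.998 | 0.039–0.042 |
| 57, 7 | no change | no change | 0 |
| 70, 7 | 3.988 | 3.998 | 0.010 |

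At L = 57, g = 28, setting all weights to 1 but keeping the open window gives 4 − 1.60/40 = 3.960. So the weight explains only 0.005–0.007 of the 0.020–0.022, and the extra days explain the rest.

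**Period I dropout.** If the open Maintenance row is followed, ending the window at day 71 gains 0.005–0.015 (L = 57) or 0.011–0.029 (L = 70) with g = 28. If the Washout row takes the days after day 71, there is nothing to gain.

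**Placebo-period dropout.** The assumed off-drug rate equals the placebo rate, so the record's expected rate stays at 8 and only its weight changes.

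**The case against.** The strongest case against acting is that the data may not exist. The schedule marks diary completion at Early Termination but does not say that daily entry continues after the last dose. The compliance duty in Protocol 7.5.2.1 covers Run-in to Treatment Period 2. The visit is asked for as soon as possible, and four weeks is the outer limit. A last dose on day 70 falls inside the ±3-day end-of-treatment visit window, so the larger figures need a subject who doses almost to the end, misses that visit and then records every day for four weeks. All of this stands, and it is why the size is stated as conditional.

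The planned sensitivity analyses answer part of the point. The unweighted model ("Then the ANCOVA model based on the frequency of movement disorder events during maintenance phase will be performed") and the Wilcoxon test do not use the weight, but they use the same window. The Per Protocol Set needs 0.80 × 56 = 44.8, so 45, dosing days in each Maintenance period. It can still keep a Period II dropout whose last dose is on period day 60 or later.

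A reader might infer more than the documents support:

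- **That the Period I window is plainly open too.** The Washout row covers Period I dropouts as well, so the defect there is an overlap.
- **That completers who decline the extension add a tail.** The wording would place later entries in Maintenance, but no diary is clearly scheduled for them after Week 22.
- **That a weight above 1 is an error in itself.** Weighting by diary days is ordinary precision weighting.
- **That Table 2 needs an upper limit as well.** No effect was computed for it. A limit could drop permitted Early Termination values for the 12-minute walk and CGI-I, both in the test hierarchy.

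**Conclusion.** The point holds, as a minor one. For Period II discontinuers, Table 1 as printed admits off-drug diary days after the planned 8 weeks, contrary to the endpoint description in SAP 1. For Period I dropouts the rows conflict and key terms are undefined.

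With the assumptions above, the shift is toward no difference. It is about 0.02 to 0.04 on 4.0 per late UX007 dropout in Period II with a fully recorded 28-day gap, and 0 to 0.01 with a 7-day gap. Against an SE of 1.27, even 0.04 is about 3% of one standard error. With no diary entries after period day 71 the effect is zero.

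This does not show that the primary conclusion is at risk. Nor does it show that off-drug days within the planned 8 weeks should be removed: that is an estimand choice, and ending the window at day 71 leaves those days in. At L = 57 and g = 28 the change recovers 0.020–0.022 of a shortfall of 0.045–0.047.

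**What to change.** Before unblinding, change SAP Table 1 so that:

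1. the Maintenance window ends for every subject at the planned end of that Treatment Period, meaning period day 71 or the actual end-of-treatment visit if attended, whether or not the subject goes on to the next phase;
2. later days in Period I are assigned to Washout only, so that the rows no longer overlap and the undefined term for entering washout is not needed.

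Capping the weight at 1 in SAP 8.8 is an optional tidy-up. Once the window ends it matters little, since a visit 3 days late gives 59/56 = 1.05. The primary model with the window cut at last dose may be added as a labelled sensitivity analysis. Leave the Table 2 windows as they are.

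The cost is SAP table wording and minor programming. The downside is that a few post-period diary days from non-completers go unused.

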5.2 Study Week/Treatment Week

Study weeks are the time points recorded on CRF.

For the DB treatment period, treatment weeks are defined as:

- For subjects randomized to UX007/Placebo group
 - UX007 treatment week=study week
 - Placebo treatment week=study week-12
- For subjects randomized to Placebo/UX007 group
 - Placebo treatment week=study week
 - UX007 treatment week=study week-12

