5.5 Baseline

- Movement Disorder:

Study baseline for movement disorder frequency as recorded by the subject/caregiver in diary will be normalized to a 4-week rate as

$$\frac{\text{total number of movement disorder events during the 6 weeks run-in period} \times 28}{\text{number of days with diary data during the 6 weeks run-in period}}$$

Study baseline for total duration of movement disorder in hours will be normalized to a 4-week rate as

$$\frac{\text{total duration of movement disorders in hours during the 6 weeks run-in period} \times 28}{\text{number of days with diary data during the 6 weeks run-in period}}$$

- For other efficacy endpoints, study baseline is defined as the last non-missing assessment prior to or on the date of the first dose of investigational product
- For safety endpoints, study baseline is defined as the last non-missing assessment prior to or on the date of the first dose of investigational product

Period baseline is defined as the last non-missing assessment prior to or on the date of the first dose of investigational product for each DB treatment period. A value from the first treatment period will not be considered as the period baseline for the second treatment period.

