7.4 Unscheduled or Early Termination Visits

For an unscheduled visit that occurred after the first dose date of IP, the unscheduled visit will be mapped into the closest post-baseline study scheduled visit for the assessment based on the study day of the unscheduled visit, and the target study day of the scheduled visit of the assessment in the protocol. If the unscheduled visit has the equal distance to the 2 study scheduled visits, it will be mapped to the later one.

An unscheduled visit will only be mapped to a study visit within each study period during which it occurs. For example, if an unscheduled visit occurs during the Titration period of the DB Treatment Period I, it should be mapped to the study visit in the Titration period of the DB Treatment Period I.

When there are more than one measurements mapped to the same scheduled visit (including the original measurement taken from the scheduled visit), the measurement taken on the scheduled visit will be used if it is not missing, otherwise the one closest to the target day will be used. If more than one visit has the equal distance to the target day then the later one will be used. If more than one measurement is collected on the same day, use the time or the sequence number to select the latest record. For listings and shift tables, all data points will be included.

Early termination visit will follow the same rule for unscheduled visit as described above.

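### SAP Table 2 divides Week 10 from Week 12 at a fixed Day 78/79, so an End of Treatment 1 visit 8 or more days late can lose its Period I value, and the SAP does not say whether the CRF visit label prevents this

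*SAP*

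**What the plan says.** SAP 7.3 has two window tables. Table 1 places diary data. For subjects who entered washout, its Period I maintenance window is "study day of first dose in Treatment Period I+15, the end of Treatment Period I", so it follows actual dates. Table 2 covers the rest: "For other scheduled efficacy and safety assessments the visit window assigned and the corresponding target treatment days during which an actual visit may occur is" set out there. Its relevant rows are:

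- Study Week 10 (treatment week 10 of Period I, target Day 71): "For subjects who entered into Treatment Period II ^[1] : [16, 78", with both days included; and "For subjects who did not enter into Treatment Period II: ≥16".
- Study Week 12 (treatment week 0 of Period II, target Day 85): "79, study day of first dose in Treatment Period II".
- Study Week 22: for subjects who go on to the extension, the window closes at the actual end of Period II.

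A footnote defines entry into Period II as having taken any Period II dose.

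Three other SAP sections bear on the point:

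- SAP 5.2: "Study weeks are the time points recorded on CRF". Treatment week is the study week, less 12 for the second period.
- SAP 5.5 sets the period baseline as the last available assessment up to the first dose of that period, and adds: "A value from the first treatment period will not be considered as the period baseline for the second treatment period".
- SAP 7.4 applies when several measurements map to one visit. It first takes the one from the scheduled visit if it is not missing, "otherwise the one closest to the target day will be used". Its rule that a visit stays within its own study period is written for unscheduled visits and extended to early termination visits.

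The 12MWT change and patient CGI-I are both defined at treatment week 10 and both stand in the testing sequence of SAP 8.8.2. SAP 7.2 limits analyses to observed data unless stated otherwise.

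**The concern.** A fixed study day cannot tell whether a subject is still in Period I. If the End of Treatment 1 visit slips while dosing continues, Table 2 assigns it to the first visit of the other treatment's period and leaves Week 10 empty. For the same subject, Table 1 counts diary days up to the actual end of Period I as Period I maintenance, so the two tables disagree about where Period I ends.

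The treatment of delay is also uneven. The same delay in Period II costs nothing, because Week 22 closes at an actual date. The same late visit by a subject who never crossed over stays in Week 10, because that window has no upper limit.

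At stake is the Period I value of two gatekept secondary endpoints, and of PROMIS, CANTAB, COPM and the physician scales, in a trial of about 40 subjects. If the rule is left open, someone must choose it during analysis, possibly after unblinding.

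**Working it through.** **Inputs.** Target days 71 and 85 and the windows come from SAP Table 2. The ±3-day tolerance comes from the protocol's Table 2.2. The planned 40 subjects and 15% discontinuation come from SAP 3.6.

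**The plan's boundary.** (71 + 85) / 2 = 78, so the 78/79 cut is the midpoint of the two target days.

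**Threshold.** The first day outside Week 10 is Day 79, and 79 − 71 = 8 days late. The tolerance allows Week 10 on Days 68–74 and Week 12 on Days 82–88. Since 79 − 74 = 5, the visit must be at least 5 days beyond tolerance. Visits inside tolerance are never misfiled.

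**Mapping for subjects who entered Period II** (Baseline 2 and first Period II dose 14 days after the End of Treatment 1 visit):

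| Days late | Visit day | Table 2 files it as | With actual end of Period I |
|---|---|---|---|
| 3 | 74 | Week 10 | Week 10 |
| 7 | 78 | Week 10 | Week 10 |
| 8 | 79 | Week 12 | Week 10 |
| 10 | 81 | Week 12 | Week 10 |
| 14 | 85 | Week 12 | Week 10 |

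**Worked example.** Dosing and the End of Treatment 1 visit both run to Day 80; Baseline 2 and the first Period II dose are on Day 94.

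- Table 1: diary Days 72–80 are Period I maintenance.
- Table 2: the Day 80 12MWT and CGI-I belong to Study Week 12, and Week 10 is empty unless something else was measured on Days 16–78.
- SAP 5.2: a CRF Week 10 visit is treatment week 10, and nothing is lost.
- SAP 5.5: the Period II baseline is the Day 94 value under either reading.

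**What follows if Table 2 governs.** The main analysis has no Period I value. The Wilcoxon test in SAP 8.8 ranks the difference between the two periods, so the subject has nothing to rank. The mixed model keeps the Period II value. The 12MWT sensitivity analysis in SAP 8.8.2 imputes the period baseline for a missing treatment week 10, so a measured change is replaced by zero.

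**Size.** Expected completers: 40 × 0.85 = 34. If a whole pair is lost and the standard deviation is unchanged, the standard error grows by √(n / (n − 1)):

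- n = 40: 1/40 = 2.5% of pairs; √(40/39) = 1.013.
- n = 34: 1/34 = 2.9% of pairs; √(34/33) = 1.015.
- Three pairs of 34: √(34/31) = 1.047.

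The documents give no count of affected subjects. Assuming 1 to 3, the range is about 1.3% to 4.7%.

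**The case against.** The strongest reply is that no value need be lost. The endpoints are defined at treatment week 10, and SAP 5.2 defines that term from the CRF time point. The wording of 7.3 also helps this side: it expressly maps diary data by Table 1, but describes Table 2 only as days on which a visit may occur. Relabelling is ordered in 7.4, for unscheduled and early termination visits, and there it stays within the study period. This stands as far as it goes: the loss is conditional. It does not remove the point, because 7.3 assigns windows to scheduled assessments and nothing says the CRF label overrides them.

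It is also true that the case needs a visit well outside tolerance, that a midpoint cut is a natural default, and that the primary endpoint uses Table 1. SAP 8.9 plans no statistical comparison of safety data.

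A reader might infer more than the documents support:

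- *That an on-treatment value becomes the Period II baseline.* SAP 5.5 defines that baseline from dose dates and bars first-period values.
- *That the distance rule in 7.4 picks Day 80 (5 days from Day 85) over Day 94 (9 days).* The preceding clause prefers the measurement from the scheduled visit. The scheduled Week 12 visit is Day 94 and it is not missing, so distance is not reached on the natural reading.
- *That the subject leaves every within-subject analysis.* This holds for the Wilcoxon test only.
- *That a Period II start before Day 79 bars Baseline 2 as period baseline.* The Week 12 window would indeed be empty, but treating a pre-dose washout assessment as a first-period value strains 5.5.

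**Conclusion.** The point holds as a conflict between rules with limited reach. Table 2's fixed boundary disagrees with Table 1, with its own Period II rows and with SAP 5.2. If Table 2 governs, a measured Period I treatment-week-10 value is treated as missing for any crossover subject whose on-treatment End of Treatment 1 visit falls on Day 79 or later. If 5.2 governs, the value is kept. The SAP does not say which applies.

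The damage is a missing Period I endpoint, not a biased baseline, and it does not touch the primary analysis. The size given above rests on full loss of the pair and an assumed number of subjects; in the mixed model the loss may be somewhat smaller. This is a minor correction, worth making because it is almost free and removes a choice that could otherwise be made with treatment codes known.

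**What to change.** Before unblinding, amend SAP 7.3 for subjects who entered Period II:

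1. State that a visit labelled End of Treatment 1 or Baseline 2 on the CRF keeps that label, in line with 5.2.
2. In Table 2, replace [16, 78] by [16, end of Treatment Period I], and replace the fixed Day 79 start of Week 12 by the end of Treatment Period I + 1, still closing at the first Period II dose.
3. Add a footnote that, for Table 2 only, the end of Period I is the later of the last Period I dose and the End of Treatment 1 visit.

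The restriction in item 3 matters. Table 1 uses the same phrase, which the SAP does not define, to close the primary-endpoint diary window. Carrying the new definition over could count off-drug days as maintenance, so the Table 1 window should stay as it is. One consequence should be accepted openly: an End of Treatment 1 visit held after dosing has stopped would remain Week 10.

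The cost is one sentence, two table cells and a footnote. No new data are needed, since the dose and visit dates are already used for the existing windows.
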